- **Study Physician.** This person is responsible for conducting or supervising the clinical evaluation of all participants, including physical and neurological examinations, reviewing adverse events, interpreting laboratory results; ensuring enrollment quotas and protocol adherence and for conversion determinations. The study physician will supervise project personnel and ensure that raters maintain a high level of skill and accuracy in conducting assessments.
- **Study Coordinator.** This person will be responsible for managing the day-today conduct of the trial, ensuring accurate administration of all instruments, maintaining online forms and scheduling study procedures, processing laboratory samples, serving as liaison with the clinical monitor, and coordinating clinic visits. The study coordinator may perform several ratings, including the CDR.
- **Project interviewer/Psychometrician.** This person will have at least a bachelor's degree in health care psychology, social work or a related field, and/or

well-documented experience in administering interviews and neuropsychological tests.

D.11. ADVERSE EVENTS

D.11.a. DEFINITION.

An adverse event is any adverse change from the subject's baseline condition including clinical or laboratory tests, or abnormalities that occur during the course of the study after consent.

D.11.b. FOLLOWING UP ON ADVERSE EVENTS

The investigator is obliged to follow subjects with AE's until the events have subsided, the conditions are considered medically stable, or the participants are no longer available for follow up. Subjects who discontinue due to adverse events will be treated and followed according to established medical practice. All pertinent information will be entered into the electronic CRF. All adverse events will be reported to an independent Data Safety Monitoring Board. Adverse events will be rated as mild, moderate or severe. This will also pertain to abnormal laboratory values.

Serious adverse events include any event that is fatal, life threatening, significantly or persistently disabling or incapacitating, results in hospitalization, prolongs a hospital stay, or is associated with a congenital abnormality or birth defect. In addition, any experience which the investigator regards as serious, or which would suggest significant hazard, contraindication, side effect, or precaution associated with participation in the study should be reported as a serious adverse event.

D.11.c. REPORTING SERIOUS ADVERSE EVENTS

Any such experience due to any cause, which occurs during the course of the investigation or within 30 days of the last study visit, must be reported to the Project Director within 24 hours after learning of the event. This is in turn will trigger a report to be distributed to all participating sites, IRBs, and the NIA.

D.12. STATISTICAL CONSIDERATIONS

D.12.a STUDY ASSIGNMENT

Depending on the subject's consent the subject will be enrolled in the arm with the lowest percentage of target enrollment. To ensure the minimum number of CSF samples are collected, sites will not be allowed to enroll their third participant in each arm (NL, MCI, AD) unless two of the first 3 have agreed to lumbar puncture. Extensive reporting and monitoring of enrollment progress will feed back to the ADNI-CC to ensure recruitment goals are met.

D.12.b STATISTICAL POWER

The sample sizes chosen (NL=200, MCI=400, AD=200) are designed to meet the needs of the hypotheses being tested for the proposed imaging and biochemical biomarkers.

Between-diagnostic group analyses: These analyses will mainly be confirmatory analyses to verify that the imaging measures and biomarkers behave as expected, differing across diagnostic categories in level and rate of change. An effect size in these analyses describes how the variance of the group means compares to the common variance of the observations within each group. With the chosen sample sizes, we will have 80% power to detect an effect size of 0.01, at level alpha=0.05 (0.02, at level alpha=0.01) between rates of change in the 3 clinical groups for MRI and biomarkers, 0.03 (0.04) for PET, and 0.05 (0.08) for MRI at 3 Tesla.

Within diagnostic group analyses: The primary focus of this proposal is to provide imaging and biomarker information that will help in planning future clinical trials, which are likely to be conducted within a particular diagnostic category. Therefore, we present power separately for MCI and the smaller groups of AD and normals. These analyses will have two primary goals: 1) to assess the strength of association between imaging summaries and clinical measures, and 2) to better understand the between- and within-subject variation to correlate longitudinal change in imaging with longitudinal change in clinical measures. We will have 80% power to detect an association attributed to the imaging or biomarker measures accounting for 2.1% at level alpha=0.05, (3.2%, at level alpha=0.01) of the variability in the clinical measures or imaging measures, 4.2% (6.2%) for PET, and 8.2% (11.9%) for MRI at 3 Tesla within the MCI patients and 4.2% (6.2%) for MRI, 8.2% (11.9%) for PET, and 15.4% (21.9%) for MRI at 3 Tesla within the normal or AD subjects.

We will have 80% power to detect a correlation of 0.15 at level, alpha=0.05 (0.18, at level, alpha=0.01) between MRI or biomarker and the clinical outcome, 0.21 (0.25) for PET, and 0.29 (0.35) for 3-Tesla MRI in the MCI subjects and 0.21 (0.25) for MRI, 0.29 (0.35) for PET, and 0.39 (0.47) for 3-Tesla MRI in the AD or normal subjects. Under a multivariate normal assumption, we would, for example, be able to construct 95% confidence intervals around an estimated correlation of 0.5 of the following: (0.42, 0.57) for MRI, (0.38, 0.60) for PET, and (0.33,0.64) for 3-Tesla MRI within the MCI subjects and (0.38,0.60) for MRI, (0.33,0.64) for PET, and (0.24,0.69) for 3-Tesla MRI within the normal or AD subjects.

D.12.c. STATISTICAL ANALYSES FOR HYPOTHESES

Numerous hypotheses based on the clinical and biomarker data will be evaluated. Analyses by gender and minority status will also be conducted as required by NIH policy. Five examples will be discussed here:

1. Rates of conversion from MCI to AD will average 10-15%/year. Annual conversion rates will be assessed using Kaplan-Meier product limit estimators at the conclusion of the investigation. To estimate the anticipated precision of the incidence estimates, a sensitivity analysis of the 95% confidence interval for conversion rate from MCI to AD was conducted using life table probabilities.

The 95% confidence intervals for annual conversion rate and overall conversion rate through 3 years was calculated with 2 different true conversion rates (8, 12%) and two different sample sizes (300, 400). An annual drop-out rate of 10% was assumed.

N	Annual Rate (%)	3 Year Rate (%)	3 Year Rate Confidence- Interval (%)	Half-Width (%)
300	8	22.1	16.6 - 27.6	5.5
300	12	31.9	25.7 - 38.0	6.2
400	8	22.1	17.4 - 26.9	4.7
400	12	31.9	26.5 - 37.2	5.3

It can be seen from this analysis that the MCI to AD conversion rates at three years can be anticipated to have associated 95% confidence intervals with approximately half width of 5.5%. In other words the confidence interval lower and upper bounds for either annual or 3-year rates will be within 5 percentage points of the estimated annual rate in the above 4 examples.

- 2. Baseline scores on logical memory and APOE4 status will predict conversion from MCI to AD. These two predictors will be evaluated as baseline predictors of conversion using the Cox proportional hazards model. The underlying assumptions of the model will be assessed. It is anticipated that the sample size in the MCI group will be adequate to make this assessment. A power analysis based on Pearson's correlation coefficient (transformed using Fisher's Z) to assess the power to detect a univariate predictor indicates that with 400 subjects a correlation as low as 0.2 will be detected with 94% power. A correlation of 0.2 is selected as an effect size of clinical relevance.
- 3. Measures of global functioning, such as activities of everyday living, will be more sensitive than neuropsychological measure for predicting conversion from MCI to AD. Cox modeling will be used to assess the relative predictive ability of standard global and cognitive measures.
- 4. The rate of backcrossing from MCI to normal will be extremely low for this population. The backcrossing rate will be assessed using survival analysis techniques i.e. Kaplan-Meier curves. With 400 subjects, it is anticipated that it will be possible for the rates to be estimated with confidence intervals of plus or minus five percentage points (two standard deviations) based on a sensitivity analysis.
- 5. Plasma isoprostanes will be analyzed as a potential predictor of disease state. Analysis of Covariance will be used to compare the baseline isoprostane levels between the three ADNI disease severity groups. Based on results from Pratico et al (2000, 2002), the estimated mean baseline plasma isoprostane levels for AD, MCI and Normal are .66, .44 and .19 ng/ml, respectively. The common standard deviation is estimated as 0.16. The estimated power for the omnibus comparison of isoprostane levels in the three disease severity groups is greater than .99. Other Biomarkers as

well as isoprostane will be assessed as predictors of cognitive decline. Contemporary longitudinal regression methods will be employed to assess the predictive ability of baseline isoprotane levels. Main effect assessment will be made using Generalized Estimating Equation models. Additionally potential interactions between isoprostane levels and ADNI group (AD, MCI, Normal) will be evaluated.

D.13. OVERALL STUDY TIMETABLE

This study involves 6 months of start up time, 12-18 months of enrollment and 36 months of follow up. It will therefore be active for 5 years. The first 6 months will be consumed by submission of protocol to local IRBs, verification of approval, certification of site personnel and imaging facilities in performance of the trial, establishing laboratory contracts, distribution of material to sites, preparation and implementation of training meetings and manuals, CRF and initial recruitment efforts. The recruitment will last 12-18 months with follow up of up to 36 months. After 5 years, additional data cleaning and analysis will still be ongoing.

With the extension of this protocol and the continued follow-up of subjects the ADNI study will now be active for 6 years (until September 2010). At this point the subjects who agree will be enrolled in ADNI2, if it is funded, for long-term followup.

E. INCLUSION OF WOMEN AND MINORITIES

Women and members of minority groups will be actively recruited during this protocol. Based on the participating sites data regarding enrollment of minorities, we expect 12% of subjects enrolled will be minorities. This is close to the aged minority population in the U.S. which is 14%.

F. LITERATURE CITED

- Aisen, P. S., Schafer, K., Grundman, M., Pfeiffer, E., Sano, M., Davis, K. L., et al. (2003). Results of a Multicenter Trial of Rofecoxib and Naproxen in Alzheimer's Disease. JAMA, 289(21), 2819-2826.

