Follow up visits will be carried out at six month intervals either in person or by telephone contact as proscribed in the flow sheets. A complete battery of clinical and neuropsychological measures and biomarkers will be collected at each time point that imaging studies are collected in order to correlate change on imaging studies with change in clinical measures. A lumbar puncture will be repeated at annually (in a subset of subjects). A synopsis of the study visits appear on the following pages. As part of the optional extension of study subjects, MCI and NL subjects will be asked to consent to an additional telephone check 6 months and clinic visit with collection of biomarkers and 1.5T MRI annually. Normal Controls in the PET substudy will be asked to have an annual PET scan. Any subject who previously agreed to Lumbar Puncture (LP) and who had at least a single LP will be asked to agree to additional annual Lumbar Punctures. 3T imaging will not be offered or performed after the M36 visit.

D.5.k. EARLY TERMINATION VISIT

If a subject wishes to exit the study, a termination visit will be scheduled. This will include all evaluations normally performed at the scheduled final visit.

D.5.I. UNSCHEDULED VISIT

Unscheduled visits will be discouraged. However, if needed, unscheduled visits will be tailored to the specific issue after discussion with the protocol PI.

D.5.m. RETRIEVED DROP-OUTS

Subjects missing visits will be encouraged to return for subsequent visits. Unless a subject withdraws consent, subjects who miss visits will be encouraged to come in for subsequent visits, with priority placed on the final visit.

D.5.n. PHONE CHECKS

Phone checks will occur as indicated in the schedule of events in order to maintain contact with the subject. Update demographic information and update AE information.

D.5.0. NURSING HOME PLACEMENT

If a subject is placed in a skilled nursing home, the subject status report will reflect this. All assessments will be completed, to the extent possible. If the subject withdraws consent to continue in the study, a termination visit will be conducted.

SCHEDULE OF EVENTS (NORMAL SUBJECTS)

Visit number	1	2	3	4	5	6	7	8	9	10
Visit name	Screen	Baseline								
Time (months)	0	1	6	12	18	24	30	36	42 ³	48 ³
Explain Study	Х								Х	
Obtain Consent	Х								Х	
Demographics, Family History, Inclusion and Exclusion Criteria	Х									
Medical History, Physical Exam, Neurological Exam, Hachinski	Х									

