- 1. The first 3 ml will be used for standard tests such as cell counts, glucose, and total protein with determinations done at local laboratories
- 2. The remaining CSF will be collected and processed as outlined in the Procedures manual.

All collected samples, after placement into the shipping container on dry ice (except for samples for immortalized cell lines and for ApoE genotyping both of which are shipped at room temperature) are sent the same day as collected via express mail with overnight delivery to the Penn AD Biomarker Fluid Bank Laboratory. When samples are received in the Laboratory, they will be thawed and aliquots transferred to plastic vials, bar code labeled, and placed in designated locations in the -80°C freezers. All samples will be inventoried and tracked using commercially available software. A database will be created and used for the inventory of stored samples, in conjunction with a bar code reading system. Bar code labels affixed to each sample vial will contain the following information: sample ID# (to preserve confidentiality), date of collection and processing, total initial volume collected, sample type (urine, plasma, serum, CSF), volume, aliquot number, freezer, shelf, rack, box, location in the box. A bar code label will be used on the sample tracking form that is used by the

technologist when processing and storing samples. This will be done to avoid manual entry of sample numbers in order to avoid manual entry errors. When the data are entered into the database the bar code label is scanned in and the sample aliquots entered. Removals of samples will also be tracked on the database, including the date removed and the recipient center.

D.5.s. IMAGING STUDIES

D.5.s.i. MRI SCANS

1.5 and 3T MRI scans will be collected according to a standardized protocol and transmitted to LONI at UCLA for storage. Scan time will be about 45 minutes per subject per session. See procedures manual for details of the scan collection.

D.5.s.ii. PET IMAGING PROTOCOL

- Subjects will be studied after a 4 hour fast (water only).
- Subjects will have blood glucose measured. Plasma glucose must be ≤ 180 mg/dL for FDG to be injected.
- An intravenous catheter will be placed in one arm for injection of [¹⁸F]FDG. If the quantitative protocol is used, a second i.v. catheter will be placed in the opposite arm.
- Subjects will be injected with 5.0 ± 0.5 mCi of [¹⁸F]FDG.
- One of two PET imaging protocols will be used.

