D.9.a. PET

The primary risk related to PET is that of radiation exposure. There is also minor risk associated with the venipuncture and radioisotope injection (pain and bruising or painful infiltration of a failed injection).

A subset of subjects will undergo a quantitative PET study that will require blood sampling. This sampling could result in pain or bruising.

The estimated absorbed radiation dose for [¹⁸F]-FDG (rad/mCi) for a 70kg adult is presented in the table below. These estimates were calculated from human data (Jones et al., 1982) and used the data published by the International Commission on Radiological Protection for [¹⁸F] FDG for a 70 kg adult with assumptions on biodistribution from Jones, et al, 1982 and using MIRDDOSE 2 software ("International Commission on Radiological Protection for 18[F] FDG," 1987). The critical organ is the urinary bladder wall, followed by heart, spleen and pancreas.

0			Dose to Normal		
Organ	Dose (rad/mCi)		subjects	Subjects	subjects
Bladder Wall	0.32	1.6	8	9.6	6.4
Heart Wall	0.22	1.1	5.5	6.6	4.4
Pancreas	0.096	0.48	2.4	2.88	1.92
Spleen	0.14	0.7	3.5	4.2	2.8
Lungs	0.064	0.32	1.6	1.92	1.28
Kidneys	0.074	0.37	1.85	2.22	1.48
Ovaries	0.053	0.265	1.325	1.59	1.06
Uterus	0.062	0.31	1.55	1.86	1.24
LLI Wall	0.051	0.255	1.275	1.53	1.02
Liver	0.058	0.29	1.45	1.74	1.16
Gallbladder	0.049	0.245	1.225	1.47	0.98
Small Intestine	0.047	0.235	1.175	1.41	0.94
ULI Wall	0.046	0.23	1.15	1.38	0.92
Adrenals	0.048	0.24	1.2	1.44	0.96
Testes	0.041	0.205	1.025	1.23	0.82
Red Marrow	0.047	0.235	1.175	1.41	0.94
Thymus	0.044	0.22	1.1	1.32	0.88
Thyroid	0.039	0.195	0.975	1.17	0.78
Muscle	0.039	0.195	0.975	1.17	0.78
Bone Surfaces	0.041	0.205	1.025	1.23	0.82
Breast	0.034	0.17	0.85	1.02	0.68
Skin	0.03	0.15	0.75	0.9	0.6
Brain	0.07	0.35	1.75	2.1	1.4
Other tissues	0.042	0.21	1.05	1.26	0.84

For a single 5mCi study that will be used in this project, the bladder wall will receive a dose of 1.6 rad which is still well below the dose guidelines of 5 rad published in the Code of Federal Regulations (21CFR §361.1). The protocol involves the following number of 5 mCi injections for each subject type:

AD – 4 injections (baseline, 6, 12, 24 months)

Controls – 5 injections (baseline, 6, 12, 24, 36 months)

MCI – 6 injections (baseline, 6, 12, 18, 24, 36 months)

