Thus, the entire study protocol will result in a cumulative bladder dose of 9.6 rad for MCI subjects, also well beneath the cumulative dose recommendations of 15 rad (21CFR §361.1). Doses are lower for other organs and other subject groups.

In the initial ADNI protocol we decided to limit the radiation exposure for each subject to a maximum of 35 mCi (or 7 PET studies) over the 3 year scanning period, which will keep the dosage for target organs well below acceptable limits (~ 11 rads). This permitted 1 additional PET study to be performed for quality control reasons in an MCI subject, 2 in a control subject, and 3 in an AD subject, in the event that studies need to be repeated.

D.9.a.1

Extension of PET Imaging in Normal Controls

Subjects who enrolled in the original cohort of ADNI subjects as Normal Controls will be asked to consent to annual PET scans as part of the ADNI Extension. For a single 5mCi study that will be used in this project, the bladder wall will receive a dose of 1.6 rad which is still well below the dose guidelines of 5 rad published in the Code of Federal Regulations (21CFR §361.1).

Under no circumstances may the radiation dose to an adult research subject from a single study or cumulatively from a number of studies conducted within one year be generally recognized as safe if such dose exceeds:

WHOLE BODY / ACTIVE BLOOD FORMING ORGANS / GONADs / EYE

- * Single Dose = 3 rem
- * Annual & Total Dose Commitment = 5 rem

OTHER ORGANS

- * Single Dose = 5 rem
- * Annual & Total Dose Commitment = 15 rem

The research site is responsible to report any overdosing of subjects as a protocol violation. Using real time distributed data entry and reporting, the ADCS tracks and reports on total radiation exposure for all participants in the ADNI study. The ADCS will alert the participating research sites if any subject's dosing exceeds 90% of 5/15 rad within a calendar year.

D.9.b. MRI

There are no proven biologic risks associated with MRI scanning. All subjects will be rigorously screened by MR personnel to be certain that they do not have any medical contraindications for MRI which include metallic foreign bodies in the brain or eye or cardiac pacemaker. This safety screening is part of routine clinical practice at MRI centers and is

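### The cumulative radiation figures for controls in D.9.a stop at month 36 and were not updated for the PET extension, so a control scanned at month 48 receives 9.6 rad to the bladder wall, not 8, and no less than an MCI subject

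*Protocol*

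**What the plan says.** Section D.9.a tabulates organ doses per scan and cumulatively by group. The bladder-wall row reads "Bladder Wall 0.32 1.6 8 9.6 6.4": rad per mCi, one 5 mCi scan, then controls, MCI and AD. Below the table it lists "Controls – 5 injections (baseline, 6, 12, 24, 36 months") and "MCI – 6 injections (baseline, 6, 12, 18, 24, 36 months"), with 4 injections for AD. It then gives 9.6 rad to the bladder for MCI as the result of the whole protocol and adds "Doses are lower for other organs and other subject groups".

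The same section describes a limit of 35 mCi, or 7 PET studies, set in the initial protocol for the 3-year scanning period. This left room for 1 quality-control repeat in an MCI subject, 2 in a control and 3 in an AD subject.

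The rest of the current text adds scans for controls:

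- The Schedule of Events (Normal Subjects) marks PET at baseline and months 6, 12, 24, 36 and 48. Its third footnote makes the later visits depend on funding, IRB approval and consent, and plans further years.
- Section D.5.j: "Normal Controls in the PET substudy will be asked to have an annual PET scan". D1 says the same.
- Section D.9.a.1: controls from the original cohort "will be asked to consent to annual PET scans as part of the ADNI Extension".

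For the extension, D.9.a.1 states that for one scan "the bladder wall will receive a dose of 1.6 rad". It then lists single and annual dose limits and a central alert at 90% of those limits within a calendar year. It gives no cumulative figure that includes the extension scans.

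**The concern.** The injection list and the schedule are both in force in the same document, and they count control scans differently: five against six by month 48. Appendix 2 says the protocol was updated throughout for annual control PET, but the injection list and dose column still describe the three-year schedule. Controls are the only group whose PET was extended. The MCI schedule has no PET after month 36, and the AD schedule none after month 24.

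The only cumulative dose printed for controls is therefore out of date for the very scans that need new consent and IRB approval. Anyone reading the risk section for that decision finds a total that is too low for a control who continues, next to a sentence saying that controls receive less than MCI subjects.

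**Working it through.** **Inputs.** Bladder wall 0.32 rad/mCi and 5 mCi per scan (D.9.a); 5, 6 and 4 injections for controls, MCI and AD (D.9.a); PET marks in the Schedule of Events (Normal Subjects).

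**Formula.** Cumulative dose = rad/mCi × 5 mCi × number of injections.

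**Reproducing the protocol's figures.**

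- One scan: 0.32 × 5 = 1.6 rad.
- Controls: 1.6 × 5 = 8.0 rad. MCI: 1.6 × 6 = 9.6 rad. AD: 1.6 × 4 = 6.4 rad.
- All 24 organ rows reproduce exactly with these counts, so the control column contains five scans and excludes month 48.
- Limit: 7 × 5 = 35 mCi and 7 × 1.6 = 11.2 rad, printed as about 11. Repeats: 7 − 6 = 1, 7 − 5 = 2, 7 − 4 = 3, as stated.

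**With the extension scans.**

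| Control scans | Activity | Bladder wall | Against MCI (9.6 rad) |
|---|---|---|---|
| 5 (to month 36) | 25 mCi | 8.0 rad | lower |
| 6 (month 48 added) | 30 mCi | 9.6 rad | equal |
| 7 (one further annual scan) | 35 mCi | 11.2 rad | higher |

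- Change at month 48: 9.6 / 8.0 = 1.20, or 20% above the stated dose. Other organs scale the same way; heart wall goes from 0.22 × 25 = 5.5 to 0.22 × 30 = 6.6 rad, which is also the MCI figure.
- D.5.s.ii allows a tolerance: "Subjects will be injected with 5.0 ± 0.5 mCi". At 5.5 mCi, six scans give 0.32 × 5.5 × 6 = 10.56 rad and seven give 12.32 rad. The tolerance applies equally to MCI subjects, so it does not alter the comparison between groups.

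**Against the quoted limits.** One extension scan a year gives 1.6 rad to the bladder wall, against 5 rad for a single dose and 15 rad for the annual and total commitment for such organs. Totals of 9.6 and 11.2 rad are also below 15.

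**Against the 7-study limit.** Six scheduled scans are fewer than 7, and 30 mCi is below 35 mCi.

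**The case against.** The D.9.a list and table are correct for the original three-year schedule. The month-48 scan is optional and conditional, so this could be called base text that an optional extension did not touch. D.9.a.1 does address extension exposure: it gives the per-scan dose, the dose limits, a duty to report overdosing, central tracking of total exposure and the 90% alert. The updated control total of 9.6 rad is one the protocol already accepts for MCI as well beneath 15 rad, so its safety conclusion does not change.

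All of this stands, and it limits the point to accuracy of the stated risk. It does not remove it. D.9.a presents its counts as what the protocol involves, and the schedule in force has one more control scan. The alert works by calendar year and supplies no total across years.

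A reader might go further and infer that the extension takes controls past the 7-study limit. A control who had used both permitted repeats would have 5 + 2 = 7 studies at month 36, so month 48 would be the eighth: 40 mCi and 8 × 1.6 = 12.8 rad. The document does not support calling this a breach. The limit is worded, in the past tense, for the initial protocol and its 3-year scanning period, and month 48 lies outside that period. The scheduled scans alone number six. Nothing says that any control used both repeats, and 12.8 rad is still below 15. What remains is narrower: D.9.a.1 does not say whether that limit, or the repeat allowance, carries into the extension.

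Nor can it be said that participants were given the wrong figure. The consent form is not among the material reviewed.

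**Conclusion.** The control figures are wrong as written for anyone scanned in the extension. By month 48 the cumulative bladder-wall dose is 9.6 rad instead of 8, an understatement of 1.6 rad (the correct total is 20% higher), with other organs in proportion. The statement that other groups receive less than MCI subjects then fails for these controls: the dose is equal at month 48 and higher after one more annual scan. The half of that sentence about other organs still holds.

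The month-48 result assumes only nominal 5 mCi injections and a control in the PET subset who consents to the scan. The 11.2 rad figure also assumes a further annual scan. The schedule has no column for one, although its footnote plans additional years. With D.13 ending the extended six-year study in September 2010, and taking a start in September 2004 with 6 months of start-up, only early enrollees could reach month 60.

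No quoted regulatory limit is exceeded, and no breach of the 35 mCi / 7-study limit is shown. Whether that limit applies in the extension is unstated.

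**What to change.** Reconcile D.9.a with the Schedule of Events (Normal Subjects), D1, D.5.j and D.9.a.1:

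1. Add the extension to the control injection list and the control dose column. On the schedule as it stands this is 6 injections by month 48, 30 mCi and 9.6 rad to the bladder wall, other organs in proportion, and 1.6 rad to the bladder wall for each further scan. Marking the first five as the original protocol and the rest as optional extension keeps both totals visible.
2. Correct the sentence comparing MCI with the other groups.
3. State how the scope of the 35 mCi / 7-study limit and the repeat allowance in D.9.a relates to the extension in D.9.a.1 and the schedule. Which limit or scan rule should apply is for the sponsor and the responsible safety bodies; none is proposed here.

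The cost is one recalculated table column, a few sentences, and a check that the extension consent wording agrees. The stated control dose becomes less favourable. No change to data collection or analysis is needed.
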